## **10.3 Analysis Sets**

The set of randomized patients will include all patients randomly assigned to a treatment at enrollment, regardless of whether or not a patient took any study drug.

The safety analysis set will include all patients who took at least 1 dose of study drug. The full analysis set will include all patients in the safety analysis set.

## **10.4 Data Handling Conventions**

All available data will be included for evaluation. For the purpose of efficacy analysis, missing or invalid values will be imputed using data from the previous visit for individual items and scores in the questionnaires and scales. For a derived score involving multiple items, the missing or invalid individual items will be imputed first before calculating the derived scores based on the complete individual item values. These rules apply only to the visits in which the patient is currently in the study and some data or an individual item is missing. If an assessment is not done at a visit, the missing data will not be imputed. The justification for using data from the previous visit is based on medical judgment. For the SF-36 questionnaire, the Half-Scale Missing Data Estimation (Half-Scale MDE) ([Ware et al 2007](#)) method will be used to estimate the missing values for calculating the 8 health domain scales.

Missing or invalid laboratory test results will not be estimated for biomarker analysis or safety analysis.

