### **10.6.1 Primary Variable**

The primary efficacy variable is the proportion of patients achieving a combined clinical response using the SRI assessed at week 52. An SRI response is defined as a reduction from baseline in the SLEDAI-2K score of at least 4 points, no worsening in PhGA (with worsening defined as an increase in PhGA of more than 0.30 point from baseline), no new BILAG A body system score, and no more than 1 new BILAG B body system score from baseline.

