**British Isles Lupus Assessment Group 2004**

Only record items due to SLE Disease Activity & assessment refers to manifestations occurring in the last 4 weeks (compared with the previous 4 weeks). ♦♦ TO BE USED WITH THE GLOSSARY ♦♦

Scoring: ND Not Done  
 1 Improving  
 2 Same  
 3 Worse  
 4 New  
 Yes/No OR Value (where indicated)  
 indicate if not due to SLE activity  
 (default is 0 = not present)

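### Section 10.4 carries missing BILAG-2004 items forward from the previous visit although most are change codes, so organ-system grades in the week-52 SRI can be wrong

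*Protocol*

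**What the plan says.** Protocol section 10.4 sets a general rule for efficacy data: "missing or invalid values will be imputed using data from the previous visit for individual items and scores in the questionnaires and scales". For derived scores, "the missing or invalid individual items will be imputed first before calculating the derived scores based on the complete individual item values".

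Two limits follow. "These rules apply only to the visits in which the patient is currently in the study and some data or an individual item is missing", and "If an assessment is not done at a visit, the missing data will not be imputed". The stated basis is brief: "The justification for using data from the previous visit is based on medical judgment".

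One instrument is treated separately: "For the SF-36 questionnaire, the Half-Scale Missing Data Estimation (Half-Scale MDE") is used to fill its missing values. Laboratory results are exempt, but only for biomarker and safety analyses. BILAG-2004 has no rule of its own, and section 6.1 describes it as a scale, so the general rule covers it.

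On the Appendix D form, "assessment refers to manifestations occurring in the last 4 weeks (compared with the previous 4 weeks"). Items are coded 1 improving, 2 same, 3 worse or 4 new, with zero (not present) as the default, a Not Done code, and a value or Yes/No entry where indicated.

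The primary endpoint (section 10.6.1) uses BILAG through organ-system grades: "no new BILAG A body system score, and no more than 1 new BILAG B body system score from baseline". Section 10.6.3.1 counts withdrawals as nonresponders in the primary analysis and keeps last observation carried forward for a sensitivity analysis.

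**The concern.** Carrying an item forward makes sense when the item records a state that may persist. Most BILAG-2004 items record a change over a stated interval. Repeating last visit's code at this visit asserts that the same change happened again in the next interval. That is a different claim, and for one code an impossible one.

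The filled items feed the organ-system grades A to E, and those grades decide one of the three components of the week-52 SRI. At stake is the responder status of patients whose week-52 BILAG form has gaps. With 100 patients per arm, each misclassified patient moves that arm's response rate by 1 percentage point.

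**Working it through.** **Step 1. Which items are change codes.** Counted from the Appendix D form, taking an item as change-coded unless the form marks it as a value or Yes/No entry:

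- Items 1 to 77 (constitutional to ophthalmic): 77 change-coded.
- Items 78 to 89 (renal): 12 values or Yes/No.
- Items 90 to 97 (haematology): item 95 is change-coded; the other 7 are values or Yes/No.

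Total: 77 + 1 = 78 change-coded and 12 + 7 = 19 not. 78/97 = 80%.

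**Step 2. What a carried code asserts.** The week-48 form scores weeks 44–48 against weeks 40–44. The week-52 form scores weeks 48–52 against weeks 44–48. The scored windows do not overlap. The check assumes visits exactly 4 weeks apart and reads New as absent in the comparison period.

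| Code at week 48 | Present in weeks 44–48? | Codes possible at week 52 | Can the carried code be right? |
|---|---|---|---|
| 0 Not present | No | 0, 4 | Yes, but it misses a new manifestation |
| 1 Improving | Yes | 0, 1, 2, 3 | Yes, but it can hide worsening |
| 2 Same | Yes | 0, 1, 2, 3 | Yes, or wrong either way |
| 3 Worse | Yes | 0, 1, 2, 3 | Yes, but the item may be stable or resolved |
| 4 New | Yes | 0, 1, 2, 3 | Never |

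**Step 3. From item to endpoint.** Section 10.4 fills items first and derives scores afterwards, so a carried code enters the grade. The protocol does not show how item codes become grades. A wrong code can therefore change a grade, but the document does not establish when it does.

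**Step 4. The plan's power figures, for scale.** Section 10.2 claims at least 90% power for a 25-point difference and 80% for 20 points, with 100 per group, two-sided 0.05, and placebo response of 40% to 45%. Using

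power = Φ[(d√n − 1.96·√(2·p̄(1−p̄))) / √(p₁(1−p₁) + p₂(1−p₂))]

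the results are 94.9% (40% vs 65%), 95.3% (45% vs 70%), 81.2% (40% vs 60%) and 81.6% (45% vs 65%). The stated figures reproduce.

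**Step 5. Illustration under an assumption.** The protocol gives no rate of missing items. Suppose a fraction f of week-52 outcomes is misclassified equally in both arms. If only true responders are lost, each rate becomes p(1−f) and the difference d(1−f). If errors go both ways, each rate becomes p(1−f) + (1−p)f and the difference d(1−2f). For a true 20-point difference:

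| f (assumed) | Responders lost only: difference, power | Errors both ways: difference, power |
|---|---|---|
| 1% | 19.8 points, 80.4–80.8% | 19.6 points, 79.6–80.0% |
| 5% | 19.0 points, 77.1–77.2% | 18.0 points, 72.4–72.8% |
| 10% | 18.0 points, 72.4–72.9% | 16.0 points, about 62% |

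Here f counts misclassified SRI outcomes. It would be smaller than the share of forms with a missing item, since not every gap is filled wrongly and not every wrong item alters a grade.

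**The case against.** The strongest reply is that only an item code has been shown to be wrong, not the endpoint. That is correct. The word new in the SRI means a new A or B grade relative to baseline, not item code 4 relative to the preceding 4 weeks, and no mapping between the two is given. The Appendix D form is also a sample for reference only, and 19 of its items fall outside the argument.

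A reader might infer four stronger points that the document does not support:

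- **Carried Improving codes credit false improvement in the SRI.** BILAG improvement earns no SRI credit. It counts only in the secondary BILAG clinical response. Within the SRI a carried Improving could matter only by keeping a grade low and hiding a new A or B.
- **Week-48 data displace week-52 data.** Section 10.4 uses all available data and fills only missing or invalid values, in patients still in the study, where the assessment was done.
- **Incomplete forms are systematically treated better than withdrawals.** A carried New or Worse would, if anything, count against the patient. A patient who attends week 52 with most items recorded is also not equivalent to one who withdrew.
- **The rule threatens the trial's result.** The missing-item rate is unknown and probably low. At f = 1% the power for 20 points stays essentially at the stated 80%.

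It can also be said that calling undetermined cases nonresponders replaces a possible error with a deliberate one-directional one. That stands as a cost of the fix.

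What remains is that the protocol states a rule, applies it without a BILAG exception, and supports it by medical judgment alone.

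**Conclusion.** The point holds as a limited defect. Section 10.4 applies carry-forward to change-coded BILAG-2004 items, where a carried New is false by construction at 4-week visits and other carried codes may be false. Organ-system grades in the week-52 SRI can be wrong as a result. Size and direction cannot be established from the protocol.

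The form adds an ambiguity. Its zero default competes with carry-forward for a blank item, and its Not Done code sits unclearly beside the exception for assessments not done. The protocol does not say which prevails.

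The conclusion rests on BILAG-2004 counting as a scale under section 10.4, on the sample form matching the one used, and on 4-week spacing. It is a worthwhile improvement, not a threat to the design.

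**What to change.** In section 10.4:

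- Exempt change-coded BILAG-2004 items, and organ-system grades derived from them, from carry-forward.
- State whether the form's zero default applies to a blank item, and how a single item marked Not Done is handled.
- If the BILAG component of the week-52 SRI cannot be determined from the observed items, classify the patient as a nonresponder in the primary analysis. This is in line with the handling of withdrawals in section 10.6.3.1.
- Report the carry-forward version as a sensitivity analysis, where section 10.6.3.1 already places last observation carried forward.

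Deciding what is undetermined needs the grading rules, which the protocol does not reproduce but which the derivation of grades requires anyway. The cost is wording and one derivation rule, settled before unblinding. A few incomplete cases, some of them possibly true responders, become nonresponders, which slightly lowers both response rates.

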In order to ensure patient safety, patients who are determined to be treatment failures will be withdrawn from the study. Patients may be treated for treatment failure at the discretion of the investigator. Treatment failure is defined as any of the following:

- occurrence of a severe flare according to the SFI (also results in withdrawal from the study)
- increase in use of background oral corticosteroids beyond 80 mg of prednisone equivalent/week. (NOTE: Treatment of mild/moderate flare is permitted as detailed in section 5.2. The use of steroids for the treatment of a mild or moderate flare or for the treatment of conditions other than SLE will not be permitted beginning at week 44 [visit 14] through week 52 [visit 16].)
- initiation of pulse iv steroid therapy (ie, 250 to 1000 mg iv total daily dose of methylprednisolone)
- increase in the dose of immunosuppressive agents (methotrexate, azathioprine, MMF, leflunomide) above the baseline level
- initiation of new immunosuppressive therapy (cyclophosphamide, methotrexate, azathioprine, cyclosporin, tacrolimus, leflunomide, MMF)

- initiation of therapy with biologics for the treatment of SLEte, azathioprine, cyclosporin, tacrolimus, leflunomide, MMF)

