Also, if the patient is using antimalarials, methotrexate, leflunomide, MMF, or azathioprine, the start date must be at least 3 months prior to the 1st dose of study drug, and the daily dose must be stable over the 4 weeks preceding the 1st dose of study drug. Dosages of these medications should remain stable during the study. In addition, if the patient is not currently using corticosteroids, antimalarials, methotrexate, MMF, or azathioprine, the last dose (in case of previous use) must be at least 4 weeks prior to the 1st dose of study drug. For leflunomide, the stop date must be at least 8 weeks before the 1st dose of study drug, unless an adequate cholestyramine washout has been completed. (NOTE: If cholestyramine washout is performed, the last use of leflunomide must be at least 4 weeks before the 1st dose of study drug.) If used, these medications should also be indicated on the CRF. If a patient requires treatment with any of these medications for a condition other than SLE, these same restrictions, and those detailed in section 4.2, will apply.

Changes in background therapies, including use of corticosteroids as a background therapy or for treatment of a mild or moderate flare or of a condition other than SLE, should not occur beginning with week 44 (visit 14). Any tapering of medication (ie, for clinically meaningful improvement in disease activity, dose reduction, or medication discontinuation because of toxicity) should be discussed with the medical monitor. Medication holidays (eg, less than or equal to 2 weeks) for short periods because of intercurrent illness or surgical procedures may be permitted and should be discussed with the medical monitor. However, background therapies must be stable for at least 4 weeks prior to the 1st dose of study drug.

Patients will be withdrawn from the study if any of the following occur:

- an increase in use of background oral corticosteroids beyond 80 mg of prednisone equivalent/week (NOTE: Treatment of mild/moderate flare is permitted as detailed in section 5.2. The use of corticosteroids for the treatment of a mild or moderate flare or for the treatment of conditions other than SLE will not be permitted beginning at week 44 [visit 14] through week 52 [visit 16])

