## **10.6 Efficacy Analysis**

Efficacy evaluation will be based on the full analysis set (see section 10.3) that includes all patients who received at least 1 dose of the study drug.

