### **10.6.2 Secondary Variables**

Secondary efficacy variables and endpoints are as follows:

- proportion of patients achieving an SRI response at each visit during the treatment period
- proportion of patients achieving a reduction of at least 4 points in the SLEDAI-2K total score at each visit during the treatment period
- proportion of patients achieving a clinical SLEDAI-2K response at each visit during the treatment period, where the clinical response is defined as a reduction of at least 4 points in the SLEDAI-2K clinical score
- proportion of patients achieving a BILAG-2004 response at each visit during the treatment period (no new BILAG A body system score and no more than 1 new BILAG B body system score from baseline)
- proportion of patients achieving a BILAG-2004 clinical response at each visit during the treatment period (an improvement in at least 1 category from a B score to a

- C or D score, with no worsening in any other category)
- proportion of patients showing no worsening on a PhGA scale at each visit during the treatment period
  - proportion of patients achieving a reduction of 5 points in the SLEDAI-2K total score at each visit during the treatment period
  - proportion of patients achieving a reduction of 6 points in the SLEDAI-2K total score at each visit during the treatment period
  - proportion of patients achieving an SRI-5 response at each visit during the treatment period
  - proportion of patients achieving an SRI-6 response at each visit during the treatment period
  - proportion of patients showing an improvement in tender and swollen joint counts using the 28-joint count examination for pain and tenderness at each visit during the treatment period
  - SFI at each visit during the treatment period
    - time to first mild to moderate flare
    - incidence of mild to moderate flare
    - time to severe flare (NOTE: A severe flare leads to early withdrawal)
  - changes in the SDI over time (assessed at screening and weeks 24 and 52 [or final assessment])
  - absolute and relative changes in the SF-36 at weeks 12, 24, 36, and 52 (or final assessment)
  - proportion of patients with changes in steroid dose over time throughout the study.

The exploratory efficacy variables and endpoints for this study are as follows:

- changes in the biomarkers anti-dsDNA Ab, C3, and C4 at each visit during the treatment period
- changes in the following biomarkers at weeks 4, 12, 24, 36, and 52 (or final assessment):
  - ANA

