### **10.6.3 Planned Method of Analysis**

#### **10.6.3.1 Primary Efficacy Analysis**

The efficacy evaluation will be based on the full analysis set, which will include all patients who receive at least 1 dose of study drug. The statistical method to be used for the SRI is the logistic regression model with treatment and stratification factors as main factors. Patients who withdraw from the study are classified as nonresponders as measured by SRI at week 52 in the primary analysis. The SRI is linked to the model factors through the logit function. The

likelihood-ratio–based Chi-square statistics will be used for testing the treatment difference between IPP-201101 and placebo in SRI at week 52 at the significance level 0.05. The odds ratio (active/placebo) and associated 95% confidence interval will be determined from the logistic regression model.

As sensitivity analyses, the primary analysis will be repeated using another 3 imputation methods to estimate missing SRI at week 52 according to the reason for withdrawal. In the 1st method, patients who withdraw because of lack of efficacy will be classified as treatment failures assessed by SRI at week 52. For patients who withdraw because of other reasons, their missing SRI at week 52 will be estimated using the multiple imputation method (Little and Rubin, 2002). The imputation values will be drawn from the categories formed by treatment group and randomization stratum to which the patient belongs. In the 2nd method, the missing SRI at week 52 will be imputed using the last observation carried forward (LOCF) method. In the 3rd method, patients who withdraw and those completers who used prohibited medication within 8 weeks from week 52 will be classified as nonresponders.

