#### **10.6.3.2 Secondary Efficacy Analysis**

Secondary efficacy variables will be summarized using the descriptive statistics by treatment group and time point. Safety evaluations will include all patients who received at least 1 dose of study drug. Descriptive statistics will be used to summarize the safety variables.

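### By-visit secondary responder rates appear to be observed-case while treatment failures are withdrawn, so they cannot be read beside the nonresponder-based primary SRI

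*Protocol*

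**What the plan says.** Section 10.4 sets the missing-data conventions for efficacy. Missing items and scores are filled from the previous visit, with a limit: "These rules apply only to the visits in which the patient is currently in the study". For a whole assessment that was missed, the rule is "If an assessment is not done at a visit, the missing data will not be imputed".

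Section 10.6.3.1 makes one exception for withdrawals: "Patients who withdraw from the study are classified as nonresponders as measured by SRI at week 52 in the primary analysis". The three sensitivity methods in the same section also concern only missing SRI at week 52.

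Section 10.6.2 lists the by-visit secondary endpoints, starting with "proportion of patients achieving an SRI response at each visit during the treatment period" and going on to SLEDAI-2K reductions, BILAG-2004 response, absence of PhGA worsening, SRI-5 and SRI-6. Their analysis, in section 10.6.3.2, is one sentence: "Secondary efficacy variables will be summarized using the descriptive statistics by treatment group and time point". Section 10.6 says "Efficacy evaluation will be based on the full analysis set", meaning every patient with at least one dose, but no section states the denominator at each visit.

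Withdrawal is tied to outcome. Under section 3.6, "patients who are determined to be treatment failures will be withdrawn from the study", and failure covers severe flare, excess or pulse steroids, raised or new immunosuppressants, and biologics. Section 5.2 has a largely overlapping list, introduced by "Patients will be withdrawn from the study if any of the following occur". Section 3.11.4 places the final evaluation of withdrawn patients at their last visit, so they have no assessments after it.

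**The concern.** Taken together, these rules treat the same kind of patient in two ways. A patient withdrawn for severe flare at week 20 is a nonresponder in the primary week 52 analysis. In the week 24 to week 48 secondary summaries the patient has no assessment, and nothing is imputed. On the natural reading the patient leaves both numerator and denominator.

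Because withdrawal follows failure by design, the patients lost are disproportionately nonresponders. Observed-case rates then rise over time as failing patients leave, even if nobody improves. The treatment difference can move either way, depending on how many withdraw in each arm. The effect is most direct for the endpoints defined by absence of worsening (PhGA, BILAG-2004), because patients withdrawn for flare are the likeliest to have worsened.

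Section 2.2 makes SRI at each visit a secondary objective. These curves will be read beside the primary result although they would follow a different rule.

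**Working it through.** **The plan's own figure.** Section 10.2 states, for 100 evaluable patients per group, two-sided alpha 0.05 and a placebo rate of 40% to 45%, power of at least 90% for a 25-point difference and 80% for 20 points. A pooled-variance normal approximation gives 94.9% (placebo 40%) and 95.3% (placebo 45%) for 25 points, and 81.2% and 81.6% for 20 points. The stated power reproduces. The present point does not depend on it; section 10.2 only supplies plausible response rates.

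**Inputs.**
- Placebo response 40%, the lower end of the range in section 10.2.
- Active response 60%, that is 40% plus the 20-point difference in section 10.2. Both are taken as nonresponder-imputed rates at a late visit.
- Cumulative withdrawal *w* by that visit: not in the protocol, so 10% to 30% is assumed.

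**Formula.** Of *N* treated patients, *R* respond and *wN* have withdrawn.
- Nonresponder-imputed rate = *R/N*.
- Observed-case rate = *R*/[*N*(1 − *w*)] = nonresponder-imputed rate / (1 − *w*).

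This holds because withdrawn patients contribute nothing to the numerator under either rule and leave the denominator only under the observed-case rule. It assumes that everyone still in the study is assessed.

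The inflation factor 1/(1 − *w*) is 1/0.9 = 1.11, 1/0.8 = 1.25 and 1/0.7 = 1.43.

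**Results.**

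| Imputed rates (placebo vs active) | Withdrawn (placebo / active) | Observed-case rates | Difference shown |
|---|---|---|---|
| 40% vs 60% (20 points) | 10% / 10% | 44.4% vs 66.7% | 22.2 points |
| 40% vs 60% | 20% / 20% | 50.0% vs 75.0% | 25.0 points |
| 40% vs 60% | 30% / 30% | 57.1% vs 85.7% | 28.6 points |
| 40% vs 60% | 30% / 10% | 57.1% vs 66.7% | 9.5 points |
| 40% vs 60% | 10% / 30% | 44.4% vs 85.7% | 41.3 points |
| 40% vs 40% (0 points) | 30% / 10% | 57.1% vs 44.4% | −12.7 points |
| 40% vs 40% | 10% / 30% | 44.4% vs 57.1% | +12.7 points |

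**Effect within one arm.** Suppose 30% have withdrawn by week 48, and 40% of all treated patients respond at both week 48 and week 52. The by-visit summary shows 0.40/0.70 = 57.1% at week 48 and the primary analysis shows 40% at week 52. The apparent fall of 17.1 points comes only from the change of rule; no patient changed status.

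**The case against.** The strongest reply is that the protocol is silent on the by-visit denominator rather than wrong. Efficacy is to be evaluated on the full analysis set, without restriction to the primary endpoint. If a proportion of patients in that set means a proportion of all treated patients, a withdrawn patient simply does not count as a responder, and no imputation is needed. Denominators for descriptive tables are often left to the SAP, which is not at hand, and section 10.11 refers to a complete statistical plan. Nothing confirmatory is touched. Withdrawals by reason are tabulated (section 10.5.1) and time to severe flare is reported. Observed-case summaries are a legitimate display, and the larger swings above need a threefold imbalance in withdrawal.

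Much of this stands as a limit on severity. The secondary analyses are descriptive; not all worsening leads to withdrawal, and not all withdrawals are failures. The withdrawal rates are assumptions, and with 10% in each arm a 20-point difference shifts by only 2.2 points. The case with more withdrawal in the better-responding arm is the least natural if failure drives withdrawal.

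The reply does not remove the point. Section 10.4 is a rule the protocol chose to state for efficacy data, not a gap left for the SAP. Naming an analysis population does not set a denominator at each visit. Counting unassessed patients as nonresponders also fits badly with a rule of no imputation, and the protocol gives an explicit nonresponder rule for one endpoint at one visit only. If both readings are tenable, the text permits materially different results from the same data.

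**Conclusion.** The concern holds. On the natural reading of section 10.4, the by-visit secondary responder proportions are observed-case in a trial that withdraws treatment failures, and they are not comparable with the nonresponder-based primary SRI. The inflation factor is 1.11 to 1.43 for assumed withdrawal of 10% to 30%. A 20-point difference would show as 22.2 to 28.6 points with equal withdrawal in that range, and as 9.5 or 41.3 points with 30% in one arm and 10% in the other. With no difference in imputed rates, that same imbalance alone produces a 12.7-point gap in either direction.

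These sizes rest on assumed withdrawal rates and on SRI-type response rates from section 10.2. The loss of failing patients is partial but related to outcome. The effect is confined to estimation and interpretation of descriptive secondary endpoints. It should be corrected, but it does not threaten the primary conclusion. Confidence is medium, because the denominator is inferred rather than stated.

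**What to change.** In sections 10.4 and 10.6.3.2, or in the SAP with 10.4 amended to agree, state that for binary responder endpoints a patient who has withdrawn counts as a nonresponder at every later visit, with the full analysis set as denominator, as in the primary analysis. State also how a patient still in the study who misses a visit is counted, since that denominator would otherwise settle it by default. Present observed-case proportions as supportive, with the number assessed at each visit by arm.

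The cost is wording and programming; no new data are needed. Displayed percentages will be lower, and withdrawals unrelated to efficacy, such as pregnancy or withdrawn consent, will also count as nonresponse. The supportive observed-case figures make that visible.
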